#### **Intra-operative Evaluation:**

The following intraoperative factors will be evaluated: operative time (calculated from the insertion of the resectoscope to the final removal of all resected prostatic tissues), blood transfusion requirement, and intraoperative complications such as bleeding, capsular perforation, and transurethral resection (TUR) syndrome.

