**Statistical analysis:**

Statistical analysis was done by SPSS v26 (IBM Inc., Chicago, IL, USA). Shapiro-Wilks test and histograms were used to evaluate the normality of the distribution of data. Quantitative parametric variables were presented as mean and standard deviation (SD) and compared between the two groups utilizing unpaired Student's T- test. Quantitative non-parametric data were presented as median and interquartile range (IQR) and were analyzed by Mann-Whitney test. Qualitative variables were presented as frequency and percentage and were analyzed utilizing the Chi-square test or Fisher's exact test when appropriate. A two tailed P value  $< 0.05$  was considered statistically significant

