**Table 8: Intraoperative factors of the studied groups**

		Group 1 (n=45)	Group 2 (n=45)	P value	Mean difference or RR (95% CI)
Operative time (min)	Mean <math>\pm</math> SD	33.51 $\pm$ 11.49	40.53 $\pm$ 14.64	0.013*	-3.42(-11.15: 4.31)
	Range	15 – 60	18 – 75		
Blood transfusion		1 (2.22%)	2 (4.44%)	1	0.49(0.04:5.59)

[figure not shown]
\*Significantly different as P value  $\leq$ 0.05, CI: Confidence interval, RR: Relative risk

Operative time was significantly lower in group 1 than group 2 as (P value =0.013).

Blood transfusion was insignificantly different between both groups.

**Figure 14:** Operative time of the studied groups.

[figure not shown]
**Figure 15:** Blood transfusion of the studied groups.

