**Table 9: Complications of the studied groups**

		Group 1 (n=45)	Group 2 (n=45)	P value
Intraoperative	Capsular perforation	1 (2.22%)	2 (4.44%)	0.620
	Intraperitoneal bladder perforation	0 (0%)	1 (2.22%)	
	Blood transfusion	1 (2.22%)	2 (4.44%)	
Early postoperative	Severe irritative LUTs	4 (8.89%)	7 (15.56%)	0.506
	Clot retention	2 (4.44%)	4 (8.89%)	
	Stress incontinence	1 (2.22%)	2 (4.44%)	
	Bladder neck contracture	1 (2.22%)	2 (4.44%)	
		Group 1 (n=43)	Group 2 (n=41)	P value
Late postoperative	Stricture bulbar urethra	1 (2.33%)	2 (4.88%)	0.699
	Bladder neck contracture	1 (2.33%)	2 (4.88%)	

LUTs: Lower urinary tract symptoms

Complications (intraoperative, early and late postoperative) were insignificantly different between both groups.

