**Table 12: Relation between size of prostate groups and (preservation of ejaculation and rate of complications)**

		$\leq 60$ ml (n=51)	$>60$ ml (n=33)	P value	RR (95% CI)
Preserved ejaculation	After 3 months	25 (49.02%)	18 (54.55%)	0.621	0.9(0.59:1.37)
	After 6 months	25 (49.02%)	17 (51.52%)	0.823	0.95(0.62:1.47)
		(n=57)	(n=33)		
Intraoperative	Capsular perforation	1 (1.75%)	2 (6.06%)	0.034*	---
	Intraperitoneal bladder perforation	0 (0%)	1 (3.03%)		
	Blood transfusion	0 (0%)	3 (9.09%)		
Early postoperative	Severe irritative LUTs	5 (8.77%)	6 (18.18%)	0.488	---
	Clot retention	3 (5.26%)	3 (9.09%)		
	Stress incontinence	2 (3.51%)	1 (3.03%)		
Late postoperative	Stricture bulbar urethra	0 (0%)	3 (9.09%)	0.309	---
	Bladder neck contracture	3 (5.26%)	0 (0%)		

[figure not shown]
\*Significantly different as P value  $\leq 0.05$ , CI: Confidence interval, RR: Relative risk

Preserved ejaculation, early and late postoperative complications were insignificantly different between both groups.

[figure not shown]
Intraoperative complications were significantly lower in patients with prostate volume  $\leq 60$  ml than  $>60$  ml (P value=0.034).

**Figure 22:** Preserved ejaculation after 3 months of the studied groups.

**Figure 23:** Preserved ejaculation after 6 months of the studied groups.

[figure not shown]
**Figure 24:** Complications of the studied groups.

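### Table 12's significant difference in intraoperative complications by prostate size depends on counting transfusion as a complication and on no man being both perforated and transfused

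*Combined protocol and SAP*

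**What the plan says.** The Intra-operative Evaluation section names what will be recorded during surgery: operative time, then "blood transfusion requirement, and intraoperative complications such as bleeding, capsular perforation, and transurethral resection (TUR) syndrome". Transfusion is an item of its own, and complications follow as a separate, open-ended item.

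Table 8 keeps to this. It reports transfusion beside operative time (1/45 vs 2/45, P=1) and comments: "Blood transfusion was insignificantly different between both groups".

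Table 9 lists the same 1 vs 2 transfusions again, now as a row of the intraoperative complication block with the two perforation types, under one P value (0.620). Table 12 does the same by prostate size, with one P value of 0.034 for the block. The text under Table 12 concludes: "Intraoperative complications were significantly lower in patients with prostate volume" of 60 ml or less.

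For categorical data the Statistical analysis section provides the "Chi-square test or Fisher's exact test when appropriate", and it sets the threshold: "A two tailed P value $< 0.05$ was considered statistically significant". Neither that section nor the methods describe a comparison by prostate size.

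**The concern.** Transfusion is classified in two ways, and the documents do not say why. This matters because three of the seven intraoperative events in Table 12, and three of the six in the group above 60 ml, are transfusions.

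The layout also treats transfusion and perforation as mutually exclusive. A man who had both would have to be counted twice or lose one of his events. No text says whether any man had both.

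At stake is the only complication result that the document calls significant. If it depends on how one row is classified and on an unstated assumption about overlap, the sentence claims more than the table shows.

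**Working it through.** **Inputs.** Table 12, intraoperative block, 60 ml or less (n=57) vs above 60 ml (n=33):

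| Row | ≤60 ml | >60 ml |
|---|---|---|
| Capsular perforation | 1 | 2 |
| Intraperitoneal bladder perforation | 0 | 1 |
| Blood transfusion | 0 | 3 |
| None, by subtraction if no man has two events | 56 | 27 |

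**Step 1: reproduce the printed value.** Take the Pearson chi-square, Σ(O−E)²/E, without continuity correction, with E = row total × column total / 90.

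- Capsular perforation: E = 3×57/90 = 1.90 and 3×33/90 = 1.10; contribution 0.426 + 0.736.
- Bladder perforation: E = 0.63 and 0.37; contribution 0.633 + 1.094.
- Transfusion: E = 1.90 and 1.10; contribution 1.900 + 3.282.
- None: E = 52.57 and 30.43; contribution 0.224 + 0.387.

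The sum is 8.68 on 3 df, P=0.0338, which is the printed 0.034. Transfusion supplies 5.18 of the 8.68. All six event cells have expected counts below 5. The same method on Table 9 (1/0/1/43 vs 2/1/2/40) gives 1.775 on 3 df, P=0.620, again as printed. The tables were therefore built with transfusion as an exclusive category.

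**Step 2: separate the components.**

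- Perforations as two categories (1/0/56 vs 2/1/30): chi-square 3.01 on 2 df, P=0.22.
- Any perforation, 1/57 vs 3/33: Fisher P=0.138. This takes the three perforations above 60 ml to be in three men.
- Transfusion alone, 0/57 vs 3/33: Fisher P = C(33,3)/C(90,3) = 5456/117480 = 0.046.

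**Step 3: keep transfusion and count each man once.** At 60 ml or less, one man is affected, since nobody there was transfused. Above 60 ml, the number k of affected men is at least 3 (the three transfused men) and at most 2+1+3 = 6. Fisher's exact test for 1/57 vs k/33:

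| k | Men with more than one event (if perforations are in separate men) | Exact P |
|---|---|---|
| 3 | 3 | 0.138 |
| 4 | 2 | 0.058 |
| 5 | 1 | 0.024 |
| 6 | 0 | 0.009 |

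The result crosses 0.05 between k=4 and k=5.

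**Step 4: the same check on Table 9.** Without transfusion (1/0/44 vs 2/1/42) the chi-square P is 0.50 (exact 0.62), against 0.620 with it. Counting each man once, Group 1 has 1 or 2 affected men and Group 2 has 2 to 5. The smallest exact P over those combinations is 0.20 (1/45 vs 5/45). No reading makes the comparison of the randomised groups significant.

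**The case against.** The strongest reply is that transfusion belongs in the block. The protocol's list of complications is introduced by examples and begins with bleeding. Neither Table 9 nor Table 12 has an intraoperative bleeding row, so transfusion is the only indicator of bleeding printed there. Bladder perforation is not named in the list either, yet nobody would object to it. This stands. A reader might infer that the protocol requires transfusion to be removed and that the result is therefore not significant. The documents do not support that: a perforation-only outcome leaves out bleeding, so it is not strictly the protocol's definition either.

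A second reply is that, if no man had two events, the exact test gives P=0.009, stronger than the printed value. This is also correct. It applies both to the four printed categories and to 1/57 vs 6/33. But it rests on the absence of overlap, which is not stated.

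A reader might also infer that the row was added to obtain significance. Nothing shows this. Tables 9 and 12 use the same intraoperative rows, all counts are printed, and in Table 9 the block is far from significant. Reporting transfusion in Table 8 and again in Table 9 is repetition across tables, not double counting within one test.

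Finally, this is a non-randomised comparison on seven events, and it leaves the voiding, erectile and ejaculation results untouched. That limits the weight of the point. Two further features of the comparison call for caution and are not cured by re-tabulation: the group above 60 ml lies outside the stated inclusion range of 20–60 mL, and perforation during surgery is itself listed as an exclusion criterion.

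**Conclusion.** The concern holds in a limited form. The classification of transfusion differs between the Intra-operative Evaluation section and Table 8 on one side and Tables 9 and 12 on the other. The significance statement under Table 12 needs the transfusion row: exact P is 0.14 for perforation alone and 0.046 for transfusion alone. If transfusion is kept, which is defensible, exact P for men with any event lies anywhere from 0.009 to 0.14, according to overlap that only patient-level data can settle.

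The working does not show that prostate size makes no difference. Both components run in the same direction (perforation 1.8% vs 9.1%, transfusion 0% vs 9.1%), and with no overlap the evidence would be stronger than printed. What is unsupported is the unqualified sentence as it stands. The calculations assume that the printed counts are numbers of men and that 57 and 33 are the right denominators.

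**What to change.** In Table 12, take from patient-level data the number of men with any intraoperative event, count each man once, and test with Fisher's exact test, which the Statistical analysis section already provides. Show perforation and transfusion as separate lines with their own exact P values. State whether transfusion is part of the composite and why, since the Intra-operative Evaluation section lists it apart. Label all these prostate-size comparisons, including the component ones, as unplanned and exploratory, and reword the conclusion to match the result. Tabulate Table 9 in the same way; its conclusion stays the same.

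The cost is a re-tabulation of data already held and one rewritten sentence. The downside is that one result called significant may be lost or narrowed to transfusion.

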**Table 13: Role of volume of prostate in prediction of preservation of ejaculation after 6 months**

Cut-off	Sensitivity	Specificity	PPV	NPV	AUC	P value
>57	50%	57.14%	53.8%	53.3%	0.520	0.749

PPV: positive predictive value, NPV: negative predictive value, AUC: area under the curve.

Volume of prostate can't predict preservation of ejaculation after 6 months ( $P = 0.749$  and  $AUC = 0.520$ ) at cut-off  $>57$  with 50% sensitivity, 57.14% specificity, 53.8% PPV and 53.3% NPV.

**Figure 25:** Role of volume of prostate in prediction of preservation of ejaculation after 6 months.

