**Table 6: Prostate volume (ml) of the studied groups**

Prostate volume (ml)	Group 1 (n=45)	Group 2 (n=45)	P value	Mean difference (95% CI)
	Mean $\pm$ SD	53.69 $\pm$ 17.71		-3.42(-11.15: 4.31)
	Range	25 – 89	24 – 106	

\*Significantly different as P value  $\leq$ 0.05, PVR: Postvoid residual, Qmax: Maximum urinary flow rate, CI: Confidence interval

Prostate volume was insignificantly different between both groups.

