**Figure 16: Complications of the studied groups.**

**Table 10: Post-operative preserved ejaculation, semen volume and concentration of the studied groups**

[figure not shown]
		Group 1 (n=43)	Group 2 (n=41)	P value	Median, mean difference or RR (95% CI)
Preserved ejaculation	After 3 months	35 (81.4%)	8 (19.51%)	<0.001*	18.05(6.07:53.64)
	After 6 months	34 (79.07%)	8 (19.51%)	<0.001*	15.58(5.37:45.25)
Semen volume (mL)	After 3 months	2.37±0.78	2.01±0.58	0.223	0.362(-229: 0.953)
	After 6 months	2.41±0.78	2.49±0.73	0.797	-0.079(-0.165: 0.535)
Sperm concentration (million sperm/mL)	After 3 months	35 (13.75-82)	72 (62.75-89.25)	0.036*	37(8: 60)
	After 6 months	32.5 (13-72)	86. (76-106.75)	0.005*	54(20: 78)

\*Significantly different as P value ≤0.05, CI: Confidence interval, RR: Relative risk

[figure not shown]
Preserved ejaculation (after three and six months) were significantly higher in group 1 than group 2 (P value <0.001).

Semen volume (after three and six months) was insignificantly different between both groups.

[figure not shown]
Sperm concentration (after three and six months) was significantly lower in group 1 than group 2 (P value<0.05).

**Figure 17:** Preserved ejaculation of the studied groups.

**Figure 18:** Semen volume of the studied groups.

[figure not shown]
**Figure 19:** Sperm concentration of the studied groups.

[figure not shown]

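### Tables 12 and 13 pool two arms with 79% and 20% preserved ejaculation and ignore arm, so AUC 0.520 does not support the statement that prostate volume cannot predict preservation

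*Combined protocol and SAP*

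**What the plan says.** Table 13 gives one ROC analysis of prostate volume for preserved ejaculation at 6 months: AUC 0.520, P = 0.749, and a cut-off of >57 "with 50% sensitivity, 57.14% specificity, 53.8% PPV and 53.3% NPV". It gives no number of men and no interval. The conclusion is "Volume of prostate can't predict preservation of ejaculation after 6 months".

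Table 12 splits the men analysed for ejaculation at 60 ml, without regard to arm (51 + 33 = 84). Preservation for ≤60 ml v >60 ml is 49.02% v 54.55% at 3 months and 49.02% v 51.52% at 6 months. The 6-month RR is 0.95 (0.62 to 1.47), P = 0.823.

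Table 10 gives 6-month preservation of 34/43 (79.07%) in Group 1 and 8/41 (19.51%) in Group 2. Table 6 gives a difference in mean volume of -3.42 ml (95% CI -11.15 to 4.31), with 45 men per arm.

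The Statistical analysis section covers the t-test, the Mann-Whitney test and, for categorical data, this: "Qualitative variables were presented as frequency and percentage and were analyzed utilizing the Chi-square test or Fisher's exact test when appropriate". It describes no ROC, cut-off, size subgroup, stratified analysis or adjusted analysis.

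**The concern.** The operation is the dominant determinant of the outcome. When two arms with such different success rates are pooled, most comparisons between a preserved and a non-preserved man are also comparisons between operations. The AUC then depends heavily on how gland volumes happen to differ between arms, and only partly on whether volume matters after a given operation. The ejaculation rows of Table 12 have the same weakness.

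The negative conclusion could also be read as reassurance about larger glands. The inclusion criteria give a volume range of 20–60 mL, yet 33 of the 84 men analysed for ejaculation in Table 12 exceeded 60 ml. That mismatch is a separate matter to reconcile, but it gives the statement about volume more weight than an exploratory table would usually carry.

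**Working it through.** **1. Table 13 pools the arms.** Table 10 gives 34 + 8 = 42 preserved and 9 + 33 = 42 not preserved. With these counts:

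- sensitivity 21/42 = 50%
- specificity 24/42 = 57.14%
- PPV 21/(21 + 18) = 21/39 = 53.8%
- NPV 24/(24 + 21) = 24/45 = 53.3%

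All four match. Group 1 alone would not: with 34 preserved and 9 not, the same sensitivity and specificity give PPV = 17/(17 + 0.4286 × 9) = 17/20.86 = 81.5%.

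**2. The missing interval.** Hanley-McNeil, A = 0.52, 42 v 42:

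- Q₁ = A/(2 − A) = 0.3514; Q₂ = 2A²/(1 + A) = 0.3558; A² = 0.2704
- SE² = [0.2496 + 41(0.3514 − 0.2704) + 41(0.3558 − 0.2704)]/1764, so SE = 0.0633
- z = 0.02/0.0633 = 0.316, P = 0.752 (0.746 to 0.758 over rounding of the AUC; printed 0.749)
- 95% CI 0.52 ± 1.96 × 0.0633 = 0.396 to 0.644

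**3. What the pooled AUC compares.** There are 42 × 42 = 1764 preserved/not-preserved pairs:

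| Pair | Count | Share |
|---|---|---|
| Both in Group 1 | 34 × 9 = 306 | 17% |
| Both in Group 2 | 8 × 33 = 264 | 15% |
| Group 1 preserved v Group 2 not | 34 × 33 = 1122 | 64% |
| Group 2 preserved v Group 1 not | 8 × 9 = 72 | 4% |

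Within-arm pairs are 570/1764 = 32%. This step needs no model. The arm effect printed as RR 15.58 in Table 10 is the odds ratio, 1122/72; the risk ratio is 0.7907/0.1951 = 4.05.

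**4. How far the pooled AUC can be displaced (model).** Assume normal volumes, a common SD, and the same mean shift d (preserved minus not) in each arm. The half-width of the Table 6 interval is 7.73, so SD = 7.73/(1.987 × √(2/45)) = 18.45 ml and r = SD√2 = 26.09. With D the arm difference in mean volume (Group 1 minus Group 2):

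pooled AUC = [570 Φ(d/r) + 1122 Φ((D + d(9/43 + 8/41))/r) + 72 Φ((−D + d(34/43 + 33/41))/r)]/1764

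For d = 0 and D = −3.42: (570 × 0.5 + 1122 × 0.448 + 72 × 0.552)/1764 = 0.469.

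| D (ml) | Pooled AUC with no within-arm effect | Within-arm AUC matching pooled 0.520 |
|---|---|---|
| −11.15 | 0.402 | 0.69 |
| −3.42 | 0.469 | 0.58 |
| 0 | 0.500 | 0.53 |
| +4.31 | 0.539 | 0.47 |

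**5. Direction.** At D = −3.42, within-arm 0.60 shows as 0.533 and 0.70 as 0.599, both nearer 0.5. Within-arm 0.45 shows as 0.437 and 0.47 as 0.450, both further from 0.5. With balanced volumes, 0.60 shows as 0.565 and 0.40 as 0.435, both nearer 0.5.

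**6. Table 12.** The printed 6-month figures reproduce from 25/51 v 17/33: P = 0.823, RR 0.95 (0.62 to 1.47). The crude OR for >60 ml is (17 × 26)/(16 × 25) = 1.11. The arm split of the 33 large glands is not reported. As an illustration, taking 53.69 in the broken Table 6 row as the Group 1 mean, the normal model puts about 15 or 16 of them in Group 1. The Mantel-Haenszel OR would then lie between 1.25 and 1.71, depending on how the 17 preserved men divide. With 14 to 17 in Group 1 the range is 1.09 to 2.14. The stratified estimate cannot be recovered from the printed margins.

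**The case against.** A reader might infer that pooling understates any within-arm effect, or biases the analysis towards no relation. The documents do not support that. Step 5 shows that a small effect in the opposite direction would be overstated at the printed imbalance. At +4.31 ml, a within-arm 0.55 would show as 0.571. A true null at −3.42 ml is itself moved away from 0.50.

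A reader might also take 0.58 as the real within-arm AUC. It is one value in a range of 0.47 to 0.69. It treats as exact a volume difference that the documents call insignificant, and it carries a difference measured in 45 men per arm over to the 43 and 41 analysed.

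Three further points are fair. The Statistical analysis section plans no ROC, so this is a fault of the reported exploratory analysis and not of a planned one. No part of the documents uses Table 13 to select patients. And the remedy may not settle the question: at an AUC of 0.60 the SE is 0.103 in Group 1 (34 v 9) and 0.117 in Group 2 (8 v 33), or 0.077 combined, so an arm-stratified 0.58 would have a 95% CI of about 0.43 to 0.73.

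These points limit the claim about direction and size. They leave untouched that arm was ignored and that the conclusion is firmer than its interval allows.

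**Conclusion.** The point holds in a limited form. The pooling follows from the printed counts, and the 32% share of within-arm pairs needs no model. The pooled AUC therefore says little about volume after either operation, and may mask or distort an association in either direction. The 0.47 to 0.69 range rests on normal volumes, a common SD, a common within-arm shift, and the Table 6 difference applying to the 84 men analysed. No table gives volume by outcome within arm, so the within-arm AUC cannot be computed, and nothing printed shows that an effect exists.

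Apart from the pooling, an interval of about 0.40 to 0.64 (Hanley-McNeil) and a Table 12 RR interval of 0.62 to 1.47 leave a modest association open. The result is a failure to detect an association, not evidence that there is none. The comparison of the two operations in Table 10 is not affected.

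**What to change.** - Fit a logistic model for 6-month preservation with arm and continuous volume, and report the OR per 10 ml with its 95% CI.
- Show the ejaculation rows of Table 12 by arm at both time points, with a Mantel-Haenszel estimate and CI.
- Give any AUC within arm, with its CI and the numbers preserved and not preserved.
- Drop the >57 cut-off.
- Label the volume analyses exploratory, since the Statistical analysis section plans no ROC.
- Reword the Table 13 conclusion to say that no association was detected, and give the estimate and interval.

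The cost is a re-run on existing data. The within-arm estimates will be imprecise, particularly in Group 1 with 34 v 9, and the text should say so.
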